After providing informed consent, participants will enter a 28-day screening period. Upon completion of the screening period, participants who satisfy all the inclusion criteria and none of the exclusion criteria of this protocol will be randomized in a 2:1 allocation ratio to one of two study arms: rilzabrutinib or placebo.

Randomization will be carried out separately for the two age groups. For the adult group, stratified permuted block randomization will be implemented; for the pediatric group, dynamic randomization algorithm (minimization) will be implemented. The factors used for stratification (for adult participants), or balance (for pediatric participants) are splenectomy status (yes/no), and by severity of thrombocytopenia (Inclusion Criteria #3 platelet counts $< 15,000/\mu\text{L}$ or $\geq 15,000/\mu\text{L}$).

After randomization, participants will start a blinded treatment period of up to 25 weeks followed by an open-label period of 28 weeks during which all participants will receive rilzabrutinib, and then a 4-week safety follow-up period or long-term extension.

At the end of 12 weeks of treatment, participants will be assessed for achieving a platelet response defined as:

a) platelet count of $\geq 50,000/\mu\text{L}$ OR a platelet count between $\geq 30,000/\mu\text{L}$ and $< 50,000/\mu\text{L}$ and at least doubled from baseline at any time during the first 12 weeks and

b) absence of rescue medication in the 4 weeks prior to the elevated platelet count that meets platelet response criteria.

Figure 1 depicts the decision process for assessing response. The baseline value of platelet count is defined as the average of all the participant's Predose platelet counts (Screening and Study Day 1).

- Participants who respond will continue the blinded treatment period for a total of 24 weeks before entering the open label period.
- Participants who do not respond (including participants who receive rescue medication after 8 weeks of treatment) may discontinue from the study or enter the 28-week open label period at the end of Week 12, receiving treatment with 400 mg twice daily (BID) of rilzabrutinib. The initial study medication assignment will remain blinded.

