- l QOL Questionnaires include EQ-5D-5L, ITP-PAQ or ITP-KIT, and PGIS-Fatigue/PGIS/PGIC. ITP-PAQ, EQ-5D-5L and PGIS-Fatigue/PGIS/PGIC (in that order) will be administered for adults 18 years or older. ITP-KIT and EQ-5D-5L (in that order) will be administered for pediatric participants (see [Appendix 10.7](#) for EU [EEA countries] age ranges). **Questionnaires should be completed prior to all other study procedures and interactions with site staff.**
- m See [Appendix 10](#) for country-specific requirements.
- n Optional collection of 2 blood samples for vaccine-specific IgG in serum (see [Section 7.9.9](#) for a list of routine vaccines). The first blood sample should be collected within 6 weeks prior to each vaccine dose regimen and the second blood sample should be collected within approximately 3 to 6 weeks after the vaccine dose regimen is complete. Whenever possible, blood for vaccine-specific IgG should be collected at a scheduled visit; but may also be collected during an Unscheduled Visit. Dates of vaccination, disease, brand name of vaccine product and antigenic strain should be recorded.
- o Week 25/SD169 visit is the last visit of the blinded treatment period and may also serve as the start of the open label period.
- p For participants who will enter the open label period directly after 12 weeks of blinded treatment, they will attend the Week 13/SD85 visit which corresponds to the Week 25/SD169 visit (Table 2), this would be their last visit of the blinded treatment period and also the start of the open label period. They will follow the open label period schedule of assessments from Week 29 (Table 2) starting at their next scheduled visit for a total of 28 weeks.
- q For participants who will enter the open label period directly after 12 weeks of blinded treatment, they will follow the open label period schedule of assessments (**Week 25 to Week 53**) which means that they will be treated on the open-label part for a total of 28 weeks. After Week 53, the participants will follow the schedule of assessments according to their eligibility for the LTE period.

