- Platelet counts  $>250,000/\mu\text{L}$  (or  $>450,000/\mu\text{L}$  respectively) any time from Week 2 to Week 25 and
- Not rescued within the 4 weeks prior to the elevated platelet count ([Section 3.3.1.1](#)).

*Percent change from baseline on CS dose / TPO-RA dose*

Percent of dose change will be calculated at Week 53 (ie, Study day 365  $\pm$  3 days) and after 12 months on the LTE period (ie, Study day 701 ie, Study day 365  $\pm$  14 days).

*Proportion of participants who switch to rilzabrutinib as a monotherapy during the first year of the LTE period*

To qualify for “switching to rilzabrutinib as a monotherapy”, a participant must have stopped the concomitant ITP medication permanently during the first year of the LTE period (ie, from 1st dose during LTE up to Study day 701  $\pm$  7 days).

*Proportion of participants who decrease their CS dose  $>50\%$  relative to baseline values during the first year of the LTE*

Qualified participants are those who have CS dose decrease by  $>50\%$  from baseline during the first year of the LTE period (ie, from 1st dose during LTE up to Study day 701  $\pm$  7 days).

*Proportion of participants who manage to reduce their dose or stop TPO-RA agonists during the first year of the LTE*

Qualified participants are those who have TPO-RA agonist dose decreased or stopped during the first year of the LTE period (ie, from 1st dose during LTE up to Study day 701  $\pm$  7 days).

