**Table 12 - Analysis window definition for unscheduled measurements**

Scheduled Visit	Targeted study day (Analysis window) for Platelet Count a	Targeted study day (Analysis window) for Others b
Week n c	1+7*(n-1) (+/-3)	-
Week 5	29 (+/-3)	29 (-13, +14)
Week 9	57 (+/-3)	57 (-13, +14)
Week 13	85 (+/-3)	85 (-13, +14)
Week 17	113 (+/-3)	113 (-13, +14)
Week 21	141 (+/-3)	141 (-13, +14)
Week 25	169 (+/-3)	169 (-13, +14)
Week 29	197 (+/-3)	197 (-13, +14)
Week 33	225 (+/-3)	225 (-13, +14)
Week 37	253 (+/-3)	253 (-13, +14)
Week 41	281 (+/-3)	281 (-13, +14)
Week 45	309 (+/-3)	309 (-13, +14)
Week 49	337 (+/-3)	337 (-13, +14)
Week 53	365 (-3, +14)	365 (-13, +14)
Month 1 LTE	393 (-13, +14)	393 (-13, +14)
Month 2 LTE	421 (-13, +14)	421 (-13, +14)
Month 3 LTE	449 (-13, +14)	449 (-13, +14)

Scheduled Visit	Targeted study day (Analysis window) for Platelet Count a	Targeted study day (Analysis window) for Others b
Month 4 LTE	477 (-13, +14)	477 (-13, +14)
Month 5 LTE	505 (-13, +14)	505 (-13, +14)
Month 6 LTE	533 (-13, +14)	533 (-13, +14)
Month 7 LTE	561 (-13, +14)	561 (-13, +14)
Month 8 LTE	589 (-13, +14)	589 (-13, +14)
Month 9 LTE	617 (-13, +14)	617 (-13, +14)
Month 10 LTE	645 (-13, +14)	645 (-13, +14)
Month 11 LTE	673 (-13, +14)	673 (-13, +14)
Month 12 LTE	701 (-13, +42)	701 (-13, +42)
QX_LTE where X=1,2,3,....	701+28*3*X for X=1,2,3,.... (-41, +42)	

Study days are calculated considering Day 1 as the day of first administration of intervention (or the day of randomization for participant not exposed).

a Applicable to hematology, differential, reticulocytes. Hematology are measured weekly up to protocol Week 53, then every 4 weeks for 1 year, then quarterly afterwards.

b Applicable to parameters other than hematology, differential, reticulocytes.

c n = 2-4, 6-8, 10-12, 14-16, 18-20, 22-24, 26-28, 30-32, 34-36, 38-40, 42-44, 46-48, 50-52.

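### SAP 3.4.1 ties Week 53 and the end of the first LTE year to days counted from first dose, which do not fit participants who enter open label before Week 25

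*SAP*

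**What the plan says.** SAP Section 3.4.1 sets two time points for the percent change in corticosteroid and TPO-RA dose. The first is "Percent of dose change will be calculated at Week 53 (ie, Study day 365", with a margin of 3 days. The second is "after 12 months on the LTE period (ie, Study day 701 ie, Study day 365", with a margin of 14 days.

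The same section defines three LTE proportions: switching to rilzabrutinib alone, a corticosteroid decrease of more than 50%, and a TPO-RA reduction or stop. Each window runs from the first "dose during LTE up to Study day 701", with a margin of 7 days.

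The SAP's definition of the clock is in the footnote to Table 12: "Study days are calculated considering Day 1 as the day of first administration of intervention". I found no rule that restarts the count at open-label or LTE entry.

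The protocol provides a shorter route to open label. Under the study design in the Synopsis, participants without a platelet response "may discontinue from the study or enter the 28-week open label period at the end of Week 12". Footnote p to Protocol Table 2 says that "they will attend the Week 13/SD85 visit which corresponds to the Week 25/SD169 visit (Table 2"). Footnote q has them follow the Week 25 to Week 53 schedule, "which means that they will be treated on the open-label part for a total of 28 weeks". Protocol Section 4 also lets participants leave blinded treatment between Weeks 13 and 24 and join open label.

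**The concern.** A fixed study day marks the same point in the trial only if everyone spends the same time in blinded treatment, and here they do not. SAP Section 1.2.2.4.2 wants the dose endpoints at the end of open label and after 12 months in the LTE. For a participant who switched early, Study day 365 is neither.

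Two separate faults follow. For percent dose change, the reading is taken at the wrong point, and the Week 53 value falls in a period with different dosing rules. Before the LTE, concomitant ITP doses are to stay stable apart from safety adjustments. Within it, dose changes, retreatment and new ITP medication are allowed (Protocol Section 4; Table 3 footnote a). For the three proportions, the start is correctly placed at the first LTE dose and only the end is misplaced. The result is unequal follow-up under a label that promises one year to everyone.

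**Working it through.** **Inputs**
- Table 12 rule: the target day of Week n is 1 + 7 × (n − 1).
- Open-label period: 28 weeks, or 196 days, on either route (Protocol Synopsis and Table 2 footnote q).
- LTE visits: every 28 days in the first year (Protocol Table 3), so 12 intervals are 336 days.
- LTE entry: the nominal Week 53 visit (SAP Table 3).

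**The plan's own figures**
- Week 53 = 1 + 7 × 52 = Day 365.
- LTE month 12 = 365 + 336 = Day 701.

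Both reproduce exactly, and both assume that open label starts at Week 25, which is 1 + 7 × 24 = Day 169 (169 + 196 = 365).

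**Participant who switches at Week 13**
- Open-label start = 1 + 7 × 12 = Day 85.
- Own Week 53 and LTE entry = 85 + 196 = Day 281.
- Own LTE month 12 = 281 + 336 = Day 617.
- Study day 365 is 365 − 281 = 84 days after LTE entry, or 84 / 28 = 3 LTE months.
- Study day 701 is 701 − 281 = 420 days after LTE entry, or 420 / 28 = 15 LTE months.
- First-year window = 420 days against 336; 420 / 336 = 1.25. With the 7-day margin it is 413 to 427 days against 329 to 343.

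**Other entry points**, taking 28 weeks of open label for these participants too:

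| Open label starts | LTE entry | Own LTE month 12 | LTE entry to Day 701 | Ratio to 336 |
|---|---|---|---|---|
| Week 13 (Day 85) | 281 | 617 | 420 days | 1.25 |
| Week 17 (Day 113) | 309 | 645 | 392 days | 1.17 |
| Week 21 (Day 141) | 337 | 673 | 364 days | 1.08 |
| Week 25 (Day 169) | 365 | 701 | 336 days | 1.00 |

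If 12 months meant 365 calendar days, month 12 would fall at 281 + 365 = Day 646 for the Week 13 switcher and 365 + 365 = Day 730 for the Week 25 entrant. The gap of 84 days stays.

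**Internal contradiction.** The 12-month clause equates Study day 701 with Study day 365. These differ by 336 days, and a 14-day margin cannot reconcile them.

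**The case against.** The best defence is that the days are labels. Protocol Table 2 footnote p gives the label SD169 to a visit held at actual Day 85, so Study day 365 could likewise be a gloss on the nominal Week 53 visit. The ambiguity is real, but the defence does not rescue the text. When the SAP means nominal visits it says so: Table 3 and Section 3.1 define open-label and LTE entry by nominal protocol visit, and Section 3.3.2.1 uses protocol visit weeks. Its definition of study day runs from first dose. The three proportions also run from an actual dose date to a study day. If the nominal meaning was intended, the wording still needs correcting.

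Four stronger readings are tempting and are not supported.

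- *Scheduled LTE visits are misfiled by Table 12.* A reader might infer that an early switcher's LTE visits land on the late open-label rows. Table 12 is headed as applying to unscheduled measurements, and SAP Section 5.4 uses a scheduled measurement whenever one exists. The misallocation is clear only for unscheduled values.
- *The Week 53 dose change is contaminated by response-driven tapering.* Reductions for response need three scheduled visits over 12 weeks (Protocol Section 4). If those must fall within the LTE, tapering first becomes possible at about the 84-day point at which the value is read. The protocol does not say whether they must, so neither the amount of such tapering nor the extra time available for it can be computed.
- *The extra time favours one randomized arm.* Week 12 non-responders in either arm may switch or leave, and LTE entry then requires response in the last 8 open-label weeks. The documents do not give the make-up of this group, so no average follow-up can be stated either.
- *Efficacy conclusions are at risk.* SAP Section 3.4.2 calls the exploratory analyses mainly descriptive, without testing, and Section 3.1 bases open-label and LTE analyses on participants exposed to rilzabrutinib in each period.

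**Conclusion.** The text is wrong as written for anyone who enters open label before Week 25. For a Week 13 switcher, the Week 53 dose change is read 84 days after the end of open label, the 12-month value is read 84 days late (420 days into the LTE rather than 336), and the first-year proportions allow up to 420 days against 336, or 25% more. Later switchers have smaller offsets. The 420 days are a ceiling, because a participant may lose response or the LTE may close before Day 701.

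This rests on the Table 12 footnote governing Section 3.4.1, and on 28-day LTE months. The number of participants affected is not given. Severity is minor: the endpoints are exploratory, and no primary, key secondary or safety conclusion changes.

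**What to change.** In SAP Section 3.4.1:
- Define Week 53 as the participant's own nominal Week 53 visit: open-label day 197, with the first open-label dose as day 1 (1 + 196).
- Define both the 12-month LTE reading and the end of the first LTE year as LTE day 337, with the first LTE dose as day 1 (1 + 336).
- Delete the reference to Study day 365 from the LTE clause and keep one margin there.

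In SAP Section 5.4, use the same period-relative days when unscheduled measurements are allocated to the open-label and LTE rows of Table 12.

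The cost is a short wording change and two derived day variables. No data collection changes. Participants who enter open label at Week 25 keep Days 365 and 701.

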### **3.4.2 Main analytical approach**

Exploratory efficacy endpoints will be analyzed using the same methodology as specified for primary ([Section 3.2](#)) and secondary endpoints ([Section 3.3](#)) for similar data (continuous, proportion, or time to event). Analyses of exploratory endpoints will be mainly descriptive, with no testing.

For binary and response endpoints, frequency and percentage will be presented.

For other categorical endpoints (eg, IBLS, EQ-5D-5L, PGIS, PGIS-Fatigue, PGIC), frequency and percentage will be presented.

For continuous endpoints (eg, IBLS, ITP-PAQ, EQ-5D), descriptive summary will be provided at scheduled visits.

Please refer to [Section 3.7.3](#) for more details on COA related endpoints.

In addition, the following three predictive values of platelet count will be crossed tabulated in a performance metrics to predict the primary efficacy response ([Section 3.2.1](#)).

Predictive value of platelet count:

- $\geq 30,000/\mu\text{L}$  and  $\geq 20,000/\mu\text{L}$  above baseline during the first 13 weeks of treatment in absence of rescue medication 4 weeks prior to the elevated platelet count
- $\geq 50,000/\mu\text{L}$  any time during the first 13 weeks of treatment in absence of rescue medication 4 weeks prior to the elevated platelet count

The performance metrics will be constructed as follows, for each predictor and each definition of primary efficacy endpoint:

	Primary efficacy response achieved	Primary efficacy endpoint not achieved	Total
Predictive Value i (Y)	a	b	a + b
Predictive Value i (N)	c	d	c + d

Positive Predictive Value (PPV) and Negative Predictive Value (NPV) will be calculated as:

- $\text{PPV} = a/(a+b)$
- $\text{NPV} = d/(c+d)$

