10.3.9. Primary Efficacy Analysis

The primary analysis will compare the proportion of participants in the adult ITT population who achieve durable platelet response defined as platelet counts at or above 50,000/ μ L for \geq two-thirds of at least 8 non-missing weekly scheduled platelet measurements during the last 12 weeks of the 24-week blinded treatment period in the absence of rescue medication (provided that at least 2 non-missing weekly scheduled platelet measurements are at or above 50,000/ μ L during the last 6 weeks of the 24-week blinded treatment period) between rilzabrutinib and placebo with a Cochran-Mantel-Haenszel test using the two stratification factors at a 2-sided alpha level of 0.05 (see [Appendix 10.7](#) for a description of the primary efficacy analysis in the EU [EEA countries] and UK). Participants who do not respond in the first 12 weeks and enter the open label period will be treated as non-responders in the primary analysis. Participants who discontinue the study due to a rilzabrutinib-related AE lack of efficacy or receive rescue medication (including an increase in allowed concomitant ITP medications dose) will be considered as non-responders. Sensitivity analyses will be conducted on the primary analysis.

The primary endpoint will be analyzed for adult and pediatric participants separately.

Platelet counts conducted locally will be used for the primary endpoint analysis. Platelet counts conducted centrally at Clinic Visits will be used as a back-up for missed or non-analyzable local lab samples.

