10.3.11. Other Efficacy Analysis

All other analyses will be performed at the 0.05 level and will not be corrected for multiple comparisons, as they will be viewed and handled in the perspective of not testing a formal hypothesis. Other analyses include the following:

- Estimate the predictive value of platelet count for each of the three predictors separately or in combination:
 - $\geq 30,000/\mu\text{L}$ on Study Day 8
 - $\geq 20,000/\mu\text{L}$ above baseline on Study Day 8
 - $\geq 50,000/\mu\text{L}$ at any time over first 8 weeks of the treatment period to achieve the primary endpoint

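### SAP 3.4.2 replaces the protocol's Day 8 and 8-week predictors with two 13-week predictors that nearly repeat the Week 13 assessment, which pushes the negative predictive value upward

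*SAP*

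**What the plan says.** Protocol 10.3.11 (repeated in the Synopsis) sets the task: "Estimate the predictive value of platelet count for each of the three predictors separately or in combination". The three are a count of at least 30,000/µL on Study Day 8, a count at least 20,000/µL "above baseline on Study Day 8", and a count of at least 50,000/µL "at any time over first 8 weeks of the treatment period to achieve the primary endpoint".

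SAP 3.4.2 states that "the following three predictive values of platelet count will be crossed tabulated in a performance metrics to predict the primary efficacy response". Two bullets follow:

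- Predictor 1: at least 30,000/µL and at least 20,000/µL "above baseline during the first 13 weeks of treatment in absence of rescue medication 4 weeks prior to the elevated platelet count".
- Predictor 2: at least 50,000/µL "any time during the first 13 weeks of treatment in absence of rescue medication 4 weeks prior to the elevated platelet count".

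For each predictor, "Positive Predictive Value (PPV) and Negative Predictive Value (NPV) will be calculated as" a/(a+b) and d/(c+d). Cell c holds predictor-negative participants who achieve the primary response, and cell d holds those who do not.

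Protocol Section 4 defines the Week 13 assessment. To pass, a participant needs a count of at least 50,000/µL, or a count of 30,000 to below 50,000/µL that is at least double baseline, within the first 12 weeks and with no rescue in the preceding 4 weeks. Those who fail may enter open label or stop (Protocol Table 1, footnote b). On the primary analysis, Protocol 10.3.9 says: "Participants who do not respond in the first 12 weeks and enter the open label period will be treated as non-responders in the primary analysis".

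**The concern.** There are two problems. The first is traceability. The SAP's stated number does not match its list, no Day 8 or 8-week predictor remains, and nothing explains why. SAP version 3 is dated 18 March 2024. Protocol amendment 05, dated 15 May 2024, still carries the Day 8 and 8-week predictors, so two current documents disagree.

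The second is partial circularity. The 13-week predictors use the same rescue condition as the Week 13 assessment, similar count thresholds and almost the same window. Failing the assessment takes a participant out of blinded treatment and makes them a non-responder. For most predictor-negative participants the outcome is thus assigned from nearly the same information as the predictor. A high NPV could then be read as evidence that lack of response by Week 13 rules out durable response, although the design largely prevents the contrary from being observed.

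**Working it through.** **Inputs.** From SAP Section 4: 129 and 65 adults, assumed durable response 25% and 5%, Fisher's exact test at two-sided 0.05, stated power 95%. From Protocol Section 4 and 10.3.9 and SAP 3.1, 3.2.1 and 3.2.2: the assessment rule and the handling of those who fail it. The documents give no NPV and neither of the two quantities, q and r below, that determine it. Those two are assumptions.

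**1. The plan's own figure.** Exact power of the Fisher test for 25% versus 5% with 129 and 65 adults is 96.4%, against the stated 95%. The rates and sample sizes are consistent and serve as base rates here.

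**2. NPV of a predictor with no information.** This is 1 minus the response rate.
- Rilzabrutinib: 1 − 0.25 = 75%.
- Placebo: 1 − 0.05 = 95%.
- Pooled: expected responders 129 × 0.25 + 65 × 0.05 = 32.25 + 3.25 = 35.5; 35.5/194 = 18.3%; NPV 81.7%.

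**3. Those who fail the assessment.** If they enter open label, Protocol 10.3.9 makes them non-responders, and SAP 3.1 ends their double-blind on-treatment period at the first open-label dose. If they stop, SAP 3.2.2 counts post-treatment data as no response. Either way they cannot supply the counts that SAP 3.2.1 requires from the last 12 weeks, under either definition. They contribute zero to cell c.

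**4. Who can fill cell c.**
- Predictor 2: only participants who passed on a doubled count of 30,000 to below 50,000/µL.
- Predictor 1: write b for baseline and x for the count, in thousands. With b at most 30, any x of 50 or more is also at least b + 20, so it is predictor-positive. A passing count is predictor-negative only if max(30, 2b) ≤ x < b + 20. That needs b above 10 (from 30 < b + 20) and below 20 (from 2b < b + 20). The gap is widest at b = 15, from 30 to 35, which is 5,000/µL.
- Edge case: inclusion criterion 3 puts the two qualifying counts below 30 on average and no single count above 35. With a Day 1 count at that ceiling, the three-count baseline stays below (60 + 35)/3 = 31.7. A count from 50 to below 51.7 could then pass while predictor-negative. This is ignored below.

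**5. NPV formula.** Let q be the share of predictor-negative participants who passed the assessment, and r the durable response rate among them. Then NPV = 1 − q × r.

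| q (assumed) | r (assumed) | NPV |
|---|---|---|
| 5% | 10% | 99.5% |
| 10% | 25% | 97.5% |
| 20% | 25% | 95.0% |
| 30% | 25% | 92.5% |

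**6. What would bring NPV below 95%.** If 60% of the 194 adults are predictor-negative (116.4, assumed), cell c must exceed 0.05 × 116.4 = 5.82. That is about 6 of the 35.5 expected durable responders, or 16%, with no qualifying count by Week 13.

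**7. Illustrative simulation.** Weekly counts were simulated under four sets of assumed trajectories (durable response 29–33% versus 5–7%, Definition 2). NPV in the rilzabrutinib arm was:

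| Predictor | NPV |
|---|---|
| SAP predictors, assessment rule applied | 98.4–99.98% |
| SAP predictors, assessment rule removed | 93–99.96% |
| Protocol, at least 30,000/µL on Day 8 | 78–81% |
| Protocol, at least 20,000/µL above baseline on Day 8 | 74–77% |
| Protocol, at least 50,000/µL within 8 weeks | 92–93% |

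The rule itself added between 0.02 points (99.96% to 99.98%, predictor 1) and 6.6 points (92.99% to 99.58%, predictor 1, in the set with the latest onset of response).

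**8. PPV of predictor 1.** Take b = 25 and x = 47. The rise is 22, so the participant is predictor-positive. But 47 is below 50 and below 2b = 50, so this count does not pass the assessment. With no other qualifying count, the participant is a false positive by rule.

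**The case against.** The strongest reply is that a high NPV here would be mostly genuine. Participants with no count of 50,000/µL in 13 weeks would seldom hold that level for two-thirds of Weeks 14 to 25, and the low response rate alone gives an uninformative predictor 75% to 95%. The simulation supports this in part: with the assessment rule removed, NPV was still 93–99.96%. This stands, and it limits what can be blamed on the design.

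A reader might infer the stronger claim that NPV is fixed at or near 100% whatever the drug does. The documents do not support that. The doubled-count route keeps some predictor-negative participants in blinded treatment, q and r are unknown, and plausible values bring NPV down to about 92%. Nor is it safe to infer that PPV is clean and could simply be reported alone; step 8 shows otherwise for predictor 1.

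Three further replies have force. A Week 13 landmark still precedes the response window, which starts at Week 14, so it is an allowable choice if explained. SAP Table 11 lists changes made by protocol amendments, so the absence of an entry there is not a fault. Table 1, introduced as covering major changes from the protocol, is the natural place, though whether an exploratory table counts as major is a judgement. Finally, the SAP supersedes the protocol on methods, but that does not reconcile its own three with two.

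**Conclusion.** The point holds as one of traceability and interpretation. The protocol's three predictors have been replaced without explanation by two later ones, and the later ones share so much with the Week 13 assessment that NPV is biased upward by design. NPV would lie at about 92% to 99.5% over the assumed q (5–30%) and r (10–25%), to be read against 75% in the rilzabrutinib arm, 81.7% pooled and 95% in placebo for an uninformative predictor at the planned rates. How much of the excess comes from the assessment rule cannot be determined from the documents; under the simulated assumptions it was from almost nothing to about 7 points, largest when response starts late. Predictor 1's PPV is pulled down for some participants with baseline above 20,000/µL. The analysis is exploratory, descriptive and outside the multiplicity scheme, so the primary test, its power and the key secondary endpoints are untouched. Importance is low.

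**What to change.** In SAP 3.4.2, restore the protocol's three predictors, separately and in combination, and make the stated number match the list. Note there that the 8-week predictor also lies inside the window of the Week 13 assessment and keeps a milder form of the overlap; the Day 8 predictors largely avoid it.

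If the 13-week versions are kept:
- list them as additional and record the change, with a reason, in SAP Table 1;
- state that participants who fail the Week 13 assessment are non-responders by rule;
- report PPV and NPV among participants who passed it, by arm, with the arm's response rate alongside.

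The cost is SAP wording and a few extra table rows. No new data are needed: counts are scheduled weekly, and SAP Table 12 already maps the Week 2 visit to Study Day 8.
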